In this safety, feasibility and dose finding Phase II trial, 30 infants will be assigned to each of the 4 dose schedules^{4,88}. The aim of phase II trials is to explore different doses, evaluate safety & tolerability, and obtain early indication of efficacy⁸⁸. The dose-safety relationship is more important than the dose-efficacy one as efficacy is irrelevant if the dose is unsafe⁸⁹. Phase II trials are generally inadequate with respect to size, outcome, precision, and control of bias to provide formal proof of efficacy^{3,90}. Rather these trials provide baseline data, potential primary outcome and effect size justifying the larger, longer, and more expensive Phase III trial. *Recognizing that our Phase II trial is not powered for efficacy, sample size calculations based on precision of the estimate of the primary outcome & the null hypothesis and error rate are presented below.*

Sample Size Based on Precision for the Primary Efficacy Outcome:

The efficacy goal of Phase II studies is typically to estimate a clinical endpoint with a specified precision. The primary efficacy outcome in this study is the need for intubation & MV within 72 hours of AS. Using the normal approximation to the binomial as described by Piantadosi⁸⁸ ($w = Z_{\alpha} \times \sqrt{p(1 - p)/n}$; or more simply $n=1/w^2$ for estimated proportions (p) ranging from 0.2 to 0.8, where Z_{α} is the quantile from the normal distribution corresponding to the two-sided probability, n =sample size, w =width of the 95% confidence interval [CI] or precision), a sample size of 30 per dosing schedule group will allow evaluation of a failure rate of 0.25 - 0.4 with 95% CI of ± 0.15 to ± 0.17 (15 to 17% precision) (Table 12). The precision of this estimate is increased if we collapse the dilution groups corresponding to dose of 100 mg/kg & 200 mg/kg (<12%) or consider our entire sample of 120 subjects all of whom receive the study intervention (<9%).

Table 12: Sample Size & Precision for various proportions of primary efficacy outcome:

Sample Size	Rate	Precision for Estimating Outcome		
		95% CI		Precision
		Lower	Upper	
30 (for each dosing Schedule i.e. I, II, III, IV)	0.25	0.13	0.43	$\pm 15\%$
	0.3	0.17	0.48	$\pm 15\%$
	0.35	0.21	0.53	$\pm 16\%$
	0.40	0.25	0.58	$\pm 17\%$
60 (for each dose group 100/kg vs. 200 /kg)	0.25	0.16	0.37	$\pm 11\%$
	0.3	0.2	0.45	$\pm 12\%$
	0.35	0.24	0.48	$\pm 12\%$
	0.40	0.29	0.53	$\pm 12\%$
120 (for the whole group)	0.25	0.18	0.33	$\pm 8\%$
	0.3	0.23	0.39	$\pm 8\%$
	0.35	0.27	0.44	$\pm 8\%$
	0.40	0.32	0.49	$\pm 9\%$

Type I error of 0.05, two-tailed test

Sample Size Based on the Null Hypothesis & Error Rates:

We will also compare the primary efficacy outcome to that of historical controls. The eligibility criteria, baseline factors, clinical management protocols, criteria for NIV and MV, & outcomes in our study are similar to those of recently published clinical trials. The use of historic controls will decrease sample size, shorten duration, and enhance efficiency of our Phase II study; definitely an advantage for testing four dosing regimens in this orphan population^{1,90-94}. Additionally, since AS has been shown to be potentially beneficial, this will allow all patients to receive study medication early and non-invasively thus enhancing study feasibility.

The rate of intubation following NIV for RDS among 24-36 weeks GA PT infants is ~50%^{75,95}. We estimated a 50% relative risk reduction to be clinically significant and plausible based on our preliminary data & reports in literature. Studies of MIST during NIV in PT infants 24- 36 weeks GA with RDS show an absolute risk reduction of the need for MV of 10-50% and a relative risk reduction of 21-63% (RR 0.67, 95% CI 0.57, 0.79) with a lower treatment threshold (FiO₂≤0.45) conferring a greater advantage (RR 0.72, 95% CI 0.59, 0.87) compared to a higher threshold (FiO₂>0.45) (RR 0.55, 95% CI 0.40, 0.77)^{5,33,75,92,93,95-104}.

A sample size of 30 subjects within each dose schedule group will have 81.8% power to detect a relative risk reduction of 50% (absolute risk reduction 25%) in the primary outcome of the need for intubation in 72 hours compared to a historical control value of 0.5 in a two-tailed type I error rate of 0.05 (Table 13).

Collapsing dilution groups corresponding to dose of 100 mg/kg & 200 mg/kg or considering our entire sample of 120 subjects all of whom receive AS will allow us to detect a smaller effect size with greater power.

An alternative strategy for sample size of Phase II trials is to reduce the level of rigor required by increasing the Type I error rate to as large as 25%^{90,105}. This increases the risk of erroneously concluding that the treatment is worthy of further investigation but does not increase the risk of missing an efficacious treatment. This approach would allow us to evaluate the effect sizes in Table 13 with smaller sample sizes.

Table 13: Power for a Test of the Null Hypothesis assuming a Historical Control Value of 0.5

Sample Size	Rate	Absolute RR	Relative RR	Power
30 (for each dosing Schedule I, II, III, IV)	0.25	.25	.50	81.8%
60 (for each dose group 100/kg vs 200 /kg)	0.25	.25	.50	98.2%
	0.3	.2	.40	89.0%
120 (for the whole group)	0.25	.25	.50	99.9%
	0.3	.20	.40	99.5%
	0.35	.15	.30	91.6%

Power is for a two sided test with Type I error of 0.05

After enrollment of 32 infants in the Phase II study, it was recognized that there was difficulty in recruiting infants in the lowest GA stratum. The data monitoring committee (DMC) recommended:

- a. Re-distribution of sample size for the study (n=120) between the two higher GA strata (60 infants per stratum compared to previous sample size of 40 infants per stratum). This will allow retention of power of the sample size calculations in the original proposal for analysis in the margins.
- b. Aim to enroll additional 10-20 at least (maximum 40) patients in the lowest GA stratum to address feasibility of study intervention in this group and generate hypothesis for effect size estimate for efficacy in this stratum.

On July 21, 2016, we submitted a clarification amendment to the IRB requesting continued enrollment in Stratum I upto a maximum of 40 subjects as originally proposed till the enrollment targets for the higher two GA strata were met (approved 07-29-2016). This was based on our enrollment patterns, making it seem unlikely that we would reach our enrollment targets ahead of the timeline (30-36 months for study accrual) in the three GA strata.

In Dec 2016, we attained accrual goals for the two higher GA strata. We observed a change in enrollment patterns in the last 5 months of 2016 - we were able to enroll more infants overall and specifically more infants in Stratum I. Since we had several more months available for patient accrual on this grant, we requested an amendment allowing us to continue enrollment in the lowest stratum till Dec 09, 2017 for a maximum of 40 subjects in this stratum, whichever comes earlier. Since Stratum I subjects are most likely to benefit from this intervention, having as much data as possible about feasibility and efficacy in this GA group will be valuable in designing the future definitive Phase III randomized controlled trial.

This amendment was discussed with the FDA grant officer who recommended (02-17-2017) proceeding with amendment submission to IRB and IND review Division if the DMC concurs.

The DMC met on 02-22-2017 and recommended continuing subject accrual in the lowest GA Stratum (I) till Dec 2017. In addition, the DMC recommended continuing subject accrual in the two higher GA Strata subject to availability of resources; enrollment in excess will increase power and confidence in the results.

We proposed increasing the sample size by 40 to account for additional infants to be enrolled in the two higher GA strata till Dec 2017 or when 40 subjects have been accrued in Stratum I, whichever comes earlier. In addition we requested that the sample size for the study be increased by 20 to accommodate for current and future screen failures (estimating a maximum of 10 screen failures in the future). These two changes will increase the total sample size of the Phase II portion of the study to 220 subjects, and overall sample size of the study including the 17 subjects enrolled in the Phase I portion of the study will be 237.

1.1.11. Patient Population Available for the Single Center Phase II study:

This study will be performed primarily at HWH, a level III neonatal intensive care unit (NICU) and high risk maternal referral center. Numbers of infants 24^{0/7} – 36^{6/7} weeks GA treated for RDS are estimated from the data presented in Section 3.3.3. The goal is to enroll 120 subjects over 3 years. Given the statistics for the past 2 years an adequate population of infants is available even after considering a continued trend for declining birth rate, 10% need for intubation in delivery room and a conservative estimate of consent rate of 50%.

Table 14: Patient Population Available for Study:

GA	Admissions at HWH			Estimates of infants requiring treatment for RDS (%)*		Estimates of Projected # of infants requiring treatment for RDS at HWH (n)			
						Over 2 years		Over 3 Years	
	2011	2012	Total	Lower	Higher	Lower	Higher	Lower	Higher
24-28	76	76	152	0.38	1.00	58	152	87	228
29-32	120	103	223	0.27	0.62	60	138	90	207
33-36	462	462	924	0.10	0.18	88	166	132	249
Total	658	641	1299			206	457	309	685

* based on Table 2; shaded rows represent population of interest for this study

1.1.12. Statistical Analyses:

Data will be analyzed according to the intention-to-treat principle using SAS and PASW (IBM Inc.). We will report descriptive statistics for demographic, clinical and respiratory support data at baseline and over time for the entire sample and for the 4 dosing schedule groups (Appendix IX [Table M1, M2]). In addition, three subgroup analyses are planned – according to dose regardless of dilution (100 vs. 200 mg/kg), GA strata, nebulizer device using logistic regression incorporating an additional treatment-by-subgroup interaction term.

Analysis plan to address Aim #1 – Safety and Feasibility Assessment: Safety will be assessed by quantifying and comparing the AEs and their severity for the total sample and across the dosage/dilution groups and two types of nebulizers. Indicators include cardiorespiratory responses, blockage of NIV circuit and cerebral oxygen saturation (Appendix IX [Table M5]). Descriptive statistics (mean, standard deviation, proportion, inter-quarter range [IQR]) will be used to quantify these indicators; *confidence intervals will be preferred to hypothesis testing* as considerable imprecision is expected arising from low frequencies of these AEs³. ANOVA or *t*-test (continuous measures) and χ^2 test (categorical variables) will be used for comparative analyses though we may not find statistically significant differences. Paired *t*-test will be used to compare heart rate, respiratory rate, blood pressure, SpO₂, PCO₂, cerebral oxygenation (RCO₂, cFTOE), ACoRN score and nasal exam score before and after AS. These parameters will also be compared between infants who get intubated within 72 hours of study intervention and those who do not; and before and after intubation within subjects that get intubated. Feasibility will be assessed by quantifying and comparing the percentage of infants who tolerate the treatment procedure and responses of the clinical nurses and respiratory therapists on the feasibility questionnaire (Appendix IX [Table M6]). Because of the high inherent variability of these factors and small effect sizes, we do not expect to show significant differences between groups given our sample size. However this information will be useful in making the final decision to proceed with a Phase III RCT.

Analysis plan to address Aim #2: - Determination of Optimal Dilution and Dosage of AS: The optimum dose is one that produces low toxicity while nearly maximizing the biological response⁸⁹. The optimal dosage will be determined by comparing levels of adverse responses, feasibility items and primary and secondary efficacy treatment outcomes (rates of intubation, diagnosis of PDA, need for blood transfusions, postnatal growth, duration of respiratory support, length of hospital stay, and incidence of complications of prematurity including IVH, sepsis, pneumonia, BPD, NEC, ROP, and death) across the four dosing schedules (Appendix IX, Mock Tables). The optimal dosage/dilution will be the one with the minimum level of adverse responses and highest clinical treatment outcomes.

Analysis plan to address Aim #3 - Short-term efficacy of AS: The primary outcome variable for short-term efficacy is the need for intubation & MV within 72 hours of AS. We will estimate the unconditional probability of benefit for the four dosing schedule groups (I, II, III, IV), the 2 dose groups (100 vs. 200 mg/kg) and the entire study cohort of 120 subjects. We will also compare with reported rates of intubation in historical controls (50%). A special χ^2 test to compare sample proportion with population proportion will be conducted to test the study hypothesis that AS is efficacious. In the comparison analysis, different dosages/dilutions will also be considered as weight using the “optimal” dosage/dilution obtained from Aim #2 as reference. A significantly lower rate of intubation in infants treated with AS in this study as compared to the reported rate of ~0.5 at $p < 0.05$ level (two-sided) will be used as evidence supporting the efficacy of AS. However, it is likely we may not

have power to achieve statistically significant results. Nevertheless these preliminary efficacy data will be crucial in determining outcome measures and effect size for the definitive placebo-controlled Phase III trial.

A number of secondary outcomes will be assessed using the same methodology. Vital signs, SpO₂, FiO₂, NIV parameters (pressure, rate, flow) and ABG/CBG components (pH, PO₂, PCO₂) will be evaluated before and after study intervention (paired *t*-test) and over time (Longitudinal data analysis). Other secondary outcomes include change in surfactant activity in gastric aspirates, changes in cerebral oxygenation, diagnosis of PDA, need for blood transfusions, postnatal growth, duration of respiratory support, length of hospital stay, and incidence of complications of prematurity including IVH, sepsis, NEC, BPD, pneumonia, ROP, and death. We will describe and compare primary and secondary outcome data overall and by dosing schedule, and in three pre-planned subgroup analyses – by dose regardless of dilution (100 mg/kg vs 200 mg/kg), GA group stratum and nebulizer type, recognizing that we may observe trends of differences between groups without having power to determine statistical significance. We will report dichotomous secondary outcome data as proportions and compare the groups using χ^2 and nonparametric tests. We will report secondary continuous outcome data as mean (SD) for normally distributed data and median (interquartile range [IQR]) for skewed data, and will compare the groups by using parametric (*t*-test, ANOVA) and nonparametric tests (Mann-Whitney U test, Wilcoxon's test) as appropriate. Pairwise group comparisons of the four dosing schedule groups will also be performed, although we may lack power to detect significant differences. In a final posthoc analysis, we will compare infants who received intubation within 72 hours to those who did not to understand risk factors for intubation and their modification by study intervention. This analysis will be presented for the entire group and by dosing schedule group. In *adjusted analyses*, dosing schedule, GA group, nebulizer type, mode of NIV, antenatal steroids, and presence of PDA or IVH will be included as covariates recognizing that these analyses are exploratory and need to be interpreted cautiously. We will consider a p value of <0.05 for statistical significance. Mock tables for the planned analyses are presented in Appendix IX.

Recommendations for statistical analyses by the Data Monitoring Committee (DMC) during the conduct of the trial:

1. Additional factors associated with intubation in enrolled infants – clinical team, time of day/shift, clinical variables (e.g. sepsis, NEC)
2. Performing a survival curve analysis to present timing of intubation in infants who were intubated
3. Control for mode of ventilation at baseline and exploring a GA cutoff at which this intervention may be most beneficial.
4. Detailed caffeine data in relation to AS to be provided
5. DMC requested data for intubation rates in the three GA strata outside this clinical trial setting (as reported in the literature and at Hutzel Women's Hospital by initiating an observational study) as there is no placebo group in this analysis
6. Handling of infants that exited study prior to study intervention
 - a. DMC recommended performing a dual level analysis
 - i. The primary “intent to treat analysis” should include all enrolled subjects.
 - ii. A secondary “experimental analysis” should also be presented that only includes subjects that received study intervention.

REFERENCES:

1. International conference on harmonisation: General Considerations for Clinical Trials. *Fed Regist.* 1997;62(242):66113.
2. Piantadosi S. Clinical trials as experimental designs. In: Balding DJ, Cressie NAC, Fisher NI, et al., eds. *Clinical Trials: A Methodologic Perspective*. 2nd ed. New Jersey: John Wiley & Sons; 2005:127-165.
3. International conference on harmonisation; guidance on statistical principles for clinical trials; availability--FDA. Notice. *Fed Regist.* 1998;63(179):49583-49598.
4. Food, Drug Administration HHS. International Conference on Harmonisation; choice of control group and related issues in clinical trials; availability. Notice. *Fed Regist.* 2001;66(93):24390-24391.

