**AEROSOLIZED SURVANTA IN NEONATAL RESPIRATORY DISTRESS SYNDROME:
PHASE I/II STUDY (IND 115430)**

NCT02294630

FINAL STUDY PROTOCOL & STATISTICAL ANALYSIS PLAN

Date of last Revision: 07-31-2017

RESEARCH STRATEGY

1.1. Research Design:

1.1.1. Study Design:

This is a proposal for the Phase II portion of our unblinded Phase I/II trial^{1,2}. It is a safety, feasibility and dose finding study of AS for the treatment of RDS in spontaneously breathing PT neonates receiving NIV. To remove selection bias and control temporal trends, infants will be randomized to 4 parallel fixed dosing schedule groups^{1,2}. This Phase II study will identify 1 or 2 optimal doses, and provide additional data for safety, feasibility and early indication of efficacy that will be the basis for designing a definitive Phase III trial. Optimal dose(s) will be identified based on evidence of a significant positive trend with increasing dose, even if no two groups are significantly different^{3,4}. Equitable representation of GAs within each dose group will be achieved by stratified randomization. Equitable representation of two FDA-approved nebulizers will be achieved by using block sizes of 8. It is expected that choice of nebulizer device will not affect efficacy but may influence caregiver preference based on institutional practice and ease of administration (feasibility).

1.1.2. Inclusion Criteria:

1. Infants admitted to the NICU at Hutzel Women's Hospital (HWH)/Children's Hospital of Michigan (CHM)
2. Gestational age of 24^{0/7}-36^{6/7} weeks
3. Postnatal age \leq 24 hours
4. Clinical diagnosis of RDS based on (i) presence of at least two of the four classic symptoms (need of supplemental oxygen, tachypnea, intercostal retractions or grunting), *and* (ii) exclusion of other causes of respiratory failure (Section 3.6.4.1) *and* (iii) Clinician intent to administer surfactant if infant requires intubation
5. Respiratory support with NIV (CPAP or NIPPV or HFNC) with FiO₂ \geq 25% or PEEP \geq 4 cmH₂O or HFNC rate \geq 2 LPM for \leq 8 hours
6. Written informed consent from parent/guardian

1.1.3. Exclusion Criteria:

1. Previous receipt of surfactant
2. Infants with respiratory distress who are unstable and require immediate intubation (Section 3.6.5)
3. Active air leak syndrome (e.g. pneumothorax, pneumomediastinum)
4. Lethal congenital malformations; death anticipated within first 3 days of life; decision to withhold support

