Although four small RCTs (n = 41 to 64) have reported consistent superiority of NIPPV compared with NCPAP in reducing re-intubation rates after extubation in PT infants, these findings did not correlate with improvements in long term respiratory outcome of BPD⁴²⁻⁴⁶ and are not substantiated by more recent studies^{33,39}. When used as the primary mode of respiratory support in PT (24-34 weeks GA) infants with RDS, two small RCTs (n=76 & 84) showed lower intubation rates with NIPPV compared to NCPAP whereas two other RCTs (n=40 & 200) showed no difference in re-intubation rates; three of these four RCTs showed no difference in rates of BPD and/or death⁴⁶⁻⁵⁰. In the recently published, largest RCT (n=1009) comparing NIPPV with NCPAP in PT neonates <30 weeks GA, there was no difference in the need for re-intubation, BPD, and other clinically important outcomes between the two modes of NIV³³. In preplanned subgroup analyses, there was no difference in these outcomes when either NIPPV or NCPAP was used as the primary mode of respiratory support or following extubation. An updated meta-analysis evaluating NIPPV vs NCPAP post-extubation in PT infants *showed no advantage of NIPPV over NCPAP* for either BPD or death³⁹.

Similarly, HFNC has been used increasingly as a form of NIV in PT infants despite concerns about airway pressures generated⁵¹. Recently it has been shown that pharyngeal pressures generated by two frequently used HFNC systems ranged from 2.2 to 4.9 cmH₂O at flow rates of 2-8 LPM with an increase of 0.4-0.5 cmH₂O for each LPM flow ($r^2=0.97-0.99$)⁵². Moreover, four recent studies have shown comparability of efficacy of HFNC and NCPAP/NIPPV in PT neonates with the potential of reduced nasal trauma with HFNC^{34,36,38,40,53}. In two RCTs, compared to NCPAP, HFNC used for post-extubation respiratory support in PT infants <32 weeks GA (n=132 & 303) resulted in similar rates of extubation failure with significantly reduced nasal trauma scores^{36,40,53}. Another smaller RCT (n=49) reported that HFNC is as effective as NIPPV in preventing intubation in PT neonates <35 weeks GA when used as the primary treatment for RDS³⁸. A 4th large

RCT (n=432) demonstrated *similar efficacy and safety of HFNC as NCPAP* when applied immediately post-extubation or early as initial NIV support in neonates ≥ 28 weeks GA³⁴.

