Only short binasal prongs will be used for aerosol delivery in the NIV circuit. Since the ventilator circuit for NCPAP and NIPPV is identical, only one type of neonatal nasal prongs (INCA®) will be used. For the HFNC circuit, only the neonatal Fisher & Paykel short binasal prongs will be used. Nasal cannulas will be applied with recommendations that the prong outer diameter occupy $\sim 50\%$ of the nares internal diameter to allow free egress of flow around the cannula³⁴.

d) Number of doses of Aerosolized Surfactant & Intervals between Doses:

Infants will be eligible to receive a 2nd dose of AS 4 hours after the 1st dose of AS if there is continued need for NIV with FiO₂ $\geq 25\%$ or PEEP ≥ 4 cmH₂O or HFNC rate ≥ 2 LPM.

Since most PT infants with RDS receive ≤ 2 doses of intratracheal surfactant as standard of care, we chose 2 doses of AS as being the minimum number to assess efficacy without inordinately delaying standard of care treatment with intratracheal surfactant⁵⁸. Early trials of intratracheal surfactant used dosing intervals ranging from 1 to 12 hours based on ventilator settings. Since pulmonary delivery following aerosolisation is not precisely quantified, we will administer the 2nd dose 4 hours after the 1st if the infant meets criteria.

e) Duration of nebulization:

Time to nebulize each dose will depend upon volume of diluted surfactant, type of nebulizer, and ambient humidity and temperature. It is expected that for each dose nebulization will be <1 hour for the smallest infants and $<4-5$ hours in the largest infants. This Phase II study will provide critical information regarding time for nebulization of various doses for PT babies and will be crucial in determining tolerance of intervention both by the patient and clinical bedside caregivers. This will be one factor in selecting the optimal dose and dilution of AS for the definitive Phase III trial.

1.1.4.5. Gestational Age Group Strata:

Enrolled infants will be stratified by three GA strata (24^{0/7}-28^{6/7}; 29^{0/7} - 32^{6/7}, 33^{0/7} - 36^{6/7}) because need for intubation and MV has been reported to be higher in more immature infants along with higher co-morbidities of prematurity and mortality. Infants <24 weeks will be excluded as most are likely to receive intubation. ^{59,60}

1.1.4.6. Randomization Procedures: Assignment to Surfactant dosing schedule:

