The randomization list with treatment assignments corresponding to randomization numbers will be generated by the study statistician not involved in screening or enrollment of study subjects. The research pharmacist, also not involved in screening or enrollment, will receive the list and keep it concealed. For each infant enrolled, the research staff will obtain the treatment assignment corresponding to the infant’s randomization number from the research pharmacist by phone thus eliminating allocation bias⁶⁸.

1.1.4.8. Blinding:

All enrolled infants will receive active medication; only the research staff and pharmacist will be aware of the infants’ assigned group. Study medication will be reconstituted by research staff in a designated private space in the NICU. The clinical caregivers and subjects will be blinded to dose and dilution, although an experienced clinical caregiver may be able to guess the dose and dilution. Research staff monitoring the enrolled infants during study intervention will collect objective data thus minimizing bias. It is not possible to blind nebulizers as they are of very different configurations and covering them will interfere with monitoring during clinical care. Infants will remain on their allocated nebulizer device for the duration of the study.

1.1.4.9. Clinical Care of Enrolled Infants:

The attending neonatologist and clinical team will make all decisions for initiation of NIV support and need for intubation and/or intratracheal surfactant instillation. Consensus guidelines have been agreed upon by clinical staff based on previously published studies for consistency^{7,33,34,69-74}.

Suggested initial and maximum settings for NIV support are provided although clinicians may individualize care (Table 11)^{33,34,74}. Escalation of NIV will be recommended for increasing FiO₂ (>10% from baseline), partial pressure of CO₂ (PCO₂, >10 mmHg from baseline), or clinical respiratory distress. Weaning will be recommended for SpO₂ and PCO₂ maintained at 90-95% and <65 mmHg respectively for 4 hours in the absence of significant clinical signs of respiratory distress³⁴.

Table 11: Suggested initial and maximum settings for NIV support

Settings	NIPPV		NCPAP		HFNC	
	Initial	Max	Initial	Max	Initial	Max
rate bpm	10	40				
PIP (cm H ₂ O)	10 above PEEP	18				
PEEP (cm H ₂ O)	5-6	8	5-6	8		

FiO2 % to maintain SpO2	90-95%	90-95%	90-95%	90-95%	90-95%	90-95%
Ti Seconds	0.3-0.5	0.3-0.5				
Flow LPM	8-12	8-12	8-12	8-12	2-3	5-6

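### Infants in room air can meet the entry threshold, and baseline respiratory severity, though recorded, is in neither the planned subgroups nor the adjusted model for 72-hour intubation

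*Combined protocol and SAP*

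**What the plan says.** **Entry.** Section 1.1.2, item 5, requires "Respiratory support with NIV (CPAP or NIPPV or HFNC") "with FiO₂ \geq 25% or PEEP \geq 4 cmH₂O or HFNC rate \geq 2 LPM", for no more than 8 hours. One of the three limits is enough. Item 4 requires "presence of at least two of the four classic symptoms (need of supplemental oxygen, tachypnea, intercostal retractions or grunting"), exclusion of other causes, and an intention to give surfactant if the infant is intubated. Oxygen need is one sign of four, and any two will do. Section 1.1.4.1 does not require a chest x-ray before enrolment.

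**Starting settings.** Section 1.1.4.9 states: "Suggested initial and maximum settings for NIV support are provided although clinicians may individualize care". Table 11 gives an initial PEEP of 5-6 cmH2O for NIPPV and NCPAP and an initial flow of 2-3 LPM for HFNC.

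**Severity data.** Table 9 schedules CRIB, the respiratory distress score and blood gas at baseline. Section 1.1.4.10 records respiratory support at or before enrolment, and section 1.1.12 evaluates FiO2 before and after the intervention.

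**Analysis.** Section 1.1.12 plans three subgroups: dose, gestational age stratum and nebulizer. In the adjusted analyses, "dosing schedule, GA group, nebulizer type, mode of NIV, antenatal steroids, and presence of PDA or IVH will be included as covariates". The monitoring committee's list adds mode of ventilation at baseline, a gestational age cutoff and further factors such as clinical team, shift, sepsis and NEC.

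**The concern.** A threshold that the suggested starting settings already satisfy does not limit severity at entry. The sample can run from infants in 21% oxygen to infants close to the failure criteria. How ill an infant is at entry plausibly predicts intubation within 72 hours, yet no direct measure of it is in the model.

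Two uses of the data are exposed. First, the four schedules are compared in groups planned at 30 each. A prognostic factor left out of the model costs precision, and a chance imbalance in it goes uncorrected except as far as gestational age group and NIV mode track it. Second, the overall rate is tested against a fixed 0.5. If the sample is milder than the population behind that figure, the rate can fall below 0.5 with no drug effect. Both results feed the choice of dose and effect size for Phase III.

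**Working it through.** **1. Does the threshold exclude anyone at the suggested settings?**

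| Mode | Initial setting (Table 11) | Item 5 limit | Met at FiO2 21%? |
|---|---|---|---|
| NIPPV | PEEP 5-6 | PEEP ≥4 | Yes |
| NCPAP | PEEP 5-6 | PEEP ≥4 | Yes |
| HFNC | 2-3 LPM | ≥2 LPM | Yes |

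All three modes pass. Tachypnea plus retractions satisfies the two-sign part of item 4 without oxygen need, and no other criterion sets a minimum FiO2, severity score or radiographic grade.

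**2. Is severity used in the analysis?** Baseline FiO2, ACoRN score and CRIB are absent from the three subgroups, the covariate list and the monitoring committee's list. The nearest use is the unadjusted comparison of ACoRN, SpO2 and PCO2 between intubated and non-intubated infants.

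**3. The plan's own power figure.** With the arcsine formula, power = Φ(|2·asin√0.5 − 2·asin√p|·√n − 1.96). For n = 30 and p = 0.25 this gives 81.8%, as Table 13 states. The other rows also reproduce. The arithmetic is sound; the question is whether 0.5 suits this sample.

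**4. Effect of the mix on the rate (assumed risks).** The documents give no untreated risk by FiO2. Let s be the share entering below 25% FiO2, r their risk, and 50% the risk of the rest, with no drug effect. The overall rate is s·r + (1 − s)·0.50.

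| s | r = 15% | r = 25% | r = 35% |
|---|---|---|---|
| 20% | 43% | 45% | 47% |
| 30% | 39.5% | 42.5% | 45.5% |
| 40% | 36% | 40% | 44% |
| 50% | 32.5% | 37.5% | 42.5% |

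**5. Effect on a comparison of two schedules.** If s differs by 20 points, intubation differs by 0.20 × (0.50 − r): 7 points at r = 15%, 5 at 25%, 3 at 35%.

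How likely is such a gap? Under simple binomial sampling with s = 35%, two given schedules of 30 differ by 20 points or more with probability about 14%. With 50 per schedule it is about 5%. The 50 comes from section 1.1.10: the Phase II total of 220, less 20 for screen failures, divided by 4. Stratification by gestational age lowers these chances as far as age tracks FiO2.

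For scale, the standard error of a difference between two schedules of 30 at a rate of 36% is √(2 × 0.36 × 0.64/30) = 12.4 points.

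**6. Effect on the test against 0.5.** An exact two-sided 5% test declares the rate low at 9 or fewer of 30, or 48 or fewer of 120. The chance of that with no drug effect is P(X ≤ 9) or P(X ≤ 48) at the true untreated rate:

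| True untreated rate | n = 30 | n = 120 |
|---|---|---|
| 0.50 | 2.1% | 1.8% |
| 0.45 | 6.9% | 15.6% |
| 0.40 | 17.6% | 54.0% |
| 0.35 | 35.8% | 89.2% |

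This matters only if the source of the 0.5 rate was more severely ill at entry than this sample. Section 1.1.10 asserts similarity but gives no entry severity for either population.

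**The case against.** Broad, early entry looks deliberate. Section 1.1.4.2 wants surfactant given early, and section 1.1.10 describes a safety, feasibility and dose-finding trial not powered for efficacy. Randomization leaves no expected bias between schedules. Baseline respiratory support will be tabulated by schedule, so an imbalance would be visible. Gestational age group and NIV mode are in the model, risk factors for intubation are examined after the fact, and the monitoring committee asked for intubation rates outside the trial. A shift of 3 to 7 points is about a quarter to just over half of one standard error at 30 per schedule.

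Most of this stands, and it limits the point to precision, chance imbalance and the reading of the 0.5 comparison. It does not remove it: age group and mode cannot separate 21% from 45% oxygen within a stratum and mode, and a visible imbalance is not an adjusted one.

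Three stronger readings are tempting but unsupported:

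- *That room-air infants do enter in numbers.* No count is given, Table 11 is advisory, and item 4 still applies.
- *That the HFNC limit is laxer than the PEEP limit on the plan's own figures.* Section 1.1.4.4 b) reports pharyngeal pressures "at flow rates of 2-8 LPM with an increase of" 0.4-0.5 cmH2O per LPM. Item 5 uses set PEEP, and no pharyngeal pressure at a given set PEEP is stated, so the two cannot be equated.
- *That efficacy should be concluded only for infants at 25% FiO2 or more.* That would leave the intention-to-treat population late in an unblinded trial, and nothing in the documents makes 0.5 the right comparator for that subgroup.

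**Conclusion.** The point holds in a limited form. Item 5 read with Table 11 lets infants in room air with two signs of RDS enter, so severity at entry can vary widely. Direct measures of it are collected before aerosol and then left out of the subgroups and the adjusted model. For the schedules, this is lost prognostic information and incompletely corrected chance imbalance, not expected bias. For the comparison with 0.5, a low rate may partly reflect mild entrants, and the documents do not allow the reader to judge how far.

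The size is illustrative. A 20-point difference in mix is worth 3 to 7 percentage points of intubation for assumed risks of 35% down to 15% below 25% FiO2, with 50% above. The mix itself is also unknown. The existence of the gap does not depend on these assumptions; its importance does.

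**What to change.** Leave enrolment as it is. In section 1.1.12:

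1. Add baseline FiO2 and baseline ACoRN respiratory distress score as covariates in the adjusted model for 72-hour intubation that compares schedules.
2. Report the 72-hour intubation rate, with confidence intervals, for baseline FiO2 below 25% and at or above 25% (the plan's own cut), overall and beside the intention-to-treat result. Label this descriptive. The primary conclusion stays on all randomized infants.
3. State with the 0.5 comparison that the documents give no entry severity for the source of that rate, so a lower rate may partly reflect milder infants.

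The cost is SAP wording; no new data and no change in care. The downsides are two more covariates in a model the plan already calls exploratory, and low precision within the FiO2 groups. FiO2 alone is also an imperfect measure of severity, because an infant in 21% oxygen at high PEEP counts as mild. That is a reason to include the ACoRN score and to keep the split descriptive.
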